This research will take place in four areas of London and South East England where prehospital triage for stroke has been established. The focus of the research is on prehospital ambulance care and acute care settings, including stroke and emergency departments, but will also explore the organisations within which these services sit, and the wider context, including local/regional governance and commissioning, the voluntary sector, and other patient representative groups. In preparing the research application the team engaged with ambulance service leads in England and Wales, and clinical leads in Scotland (through the National Ambulance Stroke Leads group), who confirmed no other areas have implemented services of this kind at equivalent scale. Through this engagement with wider networks, the team were made aware of activity on prehospital triage for stroke in the East of England (plans to introduce a service, beginning with a pilot), and London (aims to roll out NC London model across the city). The team have engaged with people leading this activity in each area to ensure they are aware of this research, and they will to be added to the prospective stakeholder list (discussed further under Dissemination).

The study will analyse four case sites where prehospital triage has been implemented, summarised in Table 1. While similar in terms of platform and function, these case sites vary on a number of key features of the conceptual framework, including intervention characteristics (e.g., 24/7 coverage or patient eligibility), organisational characteristics (e.g. NHS Foundation trust status and academic links), and wider context (e.g., stroke system, rurality).

Characteristics	Case site				
	East Kent	NC London	Maidstone	Darent Valley	
Intervention characteristics					
Implemented from	Apr-2020	May-2020	Oct-2020	Nov-2020	
Platform	Facetime	Facetime	Facetime	Facetime	
Eligibility for assessment	All suspected strokes ¹	All suspected strokes	All suspected strokes	Diagnostic uncertainty	
Assessor	Consultant/ registrar	Consultant/ registrar	Stroke nurse, then consultant if needed	Stroke nurse, then consultant if needed	
Hours active	24/7	24/7	Stroke nurse: 24/7 Consultant: 8am- 8pm Mon-Fri	8am-6pm Mon- Fri	

Table 1. Characteristics of case sites

Organisation characteristics				
Acute FT-status	Yes	Yes	No	No
Acute Teaching	Yes	Yes	No	No
ED & Stroke unit co- located	No	No	Yes	Yes
Ambulance service	SECAmb	LAS	SECAmb	SECAmb
Wider context				

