The analyses will focus on performance in the four case sites. For the comparative analyses of prehospital care the control cohort will include combined data from four ambulance NHS Trusts where prehospital triage services for stroke are not being used: London Ambulance Service NHS Trust (excluding NC London), South East Coast Ambulance NHS Foundation Trust (excluding East Kent, Maidstone, and Darent Valley), West Midlands Ambulance Service NHS Foundation Trust (WMAS), and North East Ambulance Service NHS Foundation Trust (NEAS). For the comparative analyses of delivery of stroke clinical interventions within hospital services the analyses will use a national control drawn from the Sentinel Stroke National Audit Programme (SSNAP). All patients submitted to these datasets will be included in prehospital and in/post hospital analyses.

Data

Table 3 presents annual activity levels in terms of prehospital care (patients who have been coded as *suspected stroke/neurological* by ambulance crews) and acute stroke care (number of

strokes reported in the national audit, the vast majority of whom are conveyed by ambulance). To enable the controlled before and after design, data covering a 40-month period (April 2019 to August 2022 inclusive) will be requested, permitting a minimum of 12 months 'before' data and minimum of 26 months 'after' data.

		Case sites			
Metric	Control ^A	East Kent	NC London	Maidstone	Darent Valley
Stroke patients treated in hospital ^B	85,549 ^c	970 ^D	1457	789 ^E	515
Ambulance calls for suspected stroke/neurological event ^F	46724	1729	2529	2620	984

Table 3.Annual activity for quantitative analysis

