These patient-level analyses will compare areas using prehospital triage (NC London, East Kent, Maidstone and Darent Valley) with other areas of England where prehospital triage is not used (hereafter referred to as the 'comparator') (Table 3), using propensity score matching (taking care to use only patient variables that should not be altered by the triage intervention, e.g. sex and age).^[32] A difference in differences (DiD) approach will be employed to understand the impact of the 'treatment effect' prehospital triage on outcomes (primary outcome: patient mortality at 90 days). DiD aims to generate causal effect estimates by comparing the change in the outcome from before to after the introduction of an intervention in the group exposed to the intervention, to the change in outcome from before to after the intervention in a group not exposed to the intervention. Provided a valid control group has been identified, the difference between the two differences can be said to represent the impact of the intervention.

As outlined above, the analysis will include a minimum of 12 months 'before' data and up to 26 months 'after' data. Given the sample sizes (Table 4), the team do not anticipate concerns about statistical power, but during the early stages of the study researchers will engage with clinical partners and data owners to understand the data in depth, and will conduct robustness tests alongside the main analyses.

Workstream timeline:

- Months 1-5: researchers work with clinical collaborators and data owners to gain a deeper understanding of the data available, specify data requests.
- Months 5-15: data requests submitted and data received to be prepared for analysis.
- Months 13-22: main analyses conducted, leaving time for integration of findings (see WS4).

Workstream 3: cost-effectiveness [RQ4; months 1-24]

In addition to understanding the effectiveness of pre-hospital triage it is also important to evaluate the cost-effectiveness of the intervention. Where possible the analyses will seek to understand if different triage systems deliver variable outcomes and costs, thereby informing any wider national scale-up.

The health economic analysis will focus on the case study sites and national and regional controls (Table 3). The analyses will draw on the same data sources as requested for Workstream 2 (Table 4), along with national reference costs and Trust estimates of service costs.

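### Control areas that the protocol reports as planning triage stay in the difference-in-differences control with no rule for adoption before August 2022, and the comparator's territory and its primary-outcome source are not settled

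*Protocol*

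**What the plan says.** **Ambulance control (prehospital outcomes).** Section 4, Case sites and controls, combines four ambulance trusts, described as trusts "where prehospital triage services for stroke are not being used: London Ambulance Service NHS Trust (excluding NC London"; the others are South East Coast (without its three case sites), West Midlands and North East.

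**Stroke control (in-hospital interventions).** In the same subsection, "the analyses will use a national control drawn from the Sentinel Stroke National Audit Programme (SSNAP". Note C to Table 3 says these national data cover England, Wales and Northern Ireland, with only the case sites' strokes taken out.

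**Inclusion rule.** "All patients submitted to these datasets will be included in prehospital and in/post hospital analyses". The Data subsection sets the window as April 2019 to August 2022.

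**Known plans elsewhere.** Section 4, Setting/context, reports activity "in the East of England (plans to introduce a service, beginning with a pilot" and in "London (aims to roll out NC London model across the city". It also says that ambulance and clinical leads confirmed no other area had a comparable service at the same scale.

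**Comparator in the analysis section.** Section 9, Workstream 2, compares the case sites "with other areas of England where prehospital triage is not used" and refers to Table 3. It describes the difference-in-differences control as a group not exposed to the intervention. Section 1 speaks instead of other parts of the UK.

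**Primary outcome.** Section 9 makes it 90-day mortality. Section 4 takes mortality from Hospital Episode Statistics linked to Office for National Statistics data. Case sites and controls names no control for that source.

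**The concern.** The difference-in-differences estimate subtracts the control group's change over time from the case sites' change. If some control patients receive the same intervention in the after period, part of the effect appears in the control change and is subtracted away. The bias is toward no effect. It would reach patient destination and job cycle time through the ambulance control, and treatment times through the national control. It would also reach mortality if the mortality control is national. The estimated effect then feeds the cost-effectiveness ratio.

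The team knew of both plans when preparing the application, before the study began in September 2021. At least the 12 months from September 2021 to August 2022 were still to run, so adoption inside the window was foreseeable.

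The second problem is that the comparator has more than one definition. Under one of them the 85,549 annual control strokes in Table 3 describe the control; under another they do not. For the primary outcome the control is not named where controls are defined.

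**Working it through.** **1. Which roll-out touches which control**

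| Area | Four-trust ambulance control | National stroke control |
|---|---|---|
| London outside NC London | included by name | included (only case sites removed) |
| East of England | not included | included (only case sites removed) |

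No sentence in the protocol removes or censors a control area that begins triage. The include-all sentence points the other way.

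**2. Size of the dilution**

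Let *f* be the share of control patients in an adopting area and *t* the share of the after period for which that area is exposed. Assume the effect there equals the case-site effect and that patient numbers are even over time. Then

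expected estimate = true effect × (1 − *f·t*), and the sample size needed is multiplied by 1/(1 − *f·t*)².

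The protocol gives neither *f* nor *t*. The ranges below are assumptions.

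| Control | Assumed *f* | Assumed *t* | Effect retained | Sample-size multiplier |
|---|---|---|---|---|
| Ambulance, low | 0.10 | 0.25 | 97.5% | 1.05 |
| Ambulance, middle | 0.20 | 0.50 | 90% | 1.23 |
| Ambulance, high | 0.50 | 1.00 | 50% | 4.0 |
| National, low | 0.05 | 0.25 | 98.8% | 1.03 |
| National, middle | 0.20 | 0.50 | 90% | 1.23 |
| National, high | 0.25 | 1.00 | 75% | 1.78 |
| Either, no start before the end of August 2022 | any | 0 | 100% | 1.00 |

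For power, take an effect detectable with 80% power at two-sided 5%, so that effect/SE = 1.960 + 0.842 = 2.802.

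- 10% dilution: 0.90 × 2.802 − 1.960 = 0.56, giving about 71% power.
- 25% dilution: 0.75 × 2.802 − 1.960 = 0.14, giving about 56% power.

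**3. Cost of removing adopting areas**

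For a proportion *p* with independent patients, SE² = *p*(1 − *p*)(1/nT0 + 1/nT1 + 1/nC0 + 1/nC1), where T and C are the case sites and control, and 0 and 1 are before and after. With the same before and after lengths in both groups, the relative change in SE depends only on the annual counts in Table 3.

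- Ambulance: case sites 1,729 + 2,529 + 2,620 + 984 = 7,862; control 46,724; ratio 5.9. Removing 40% of control calls leaves 28,034. SE ratio = √[(1/7,862 + 1/28,034)/(1/7,862 + 1/46,724)] = √1.096 = 1.047, about 5% larger.
- National strokes: case sites 970 + 1,457 + 789 + 515 = 3,731; control 85,549; ratio 22.9. Removing 25% leaves 64,162. SE ratio = √[(1/3,731 + 1/64,162)/(1/3,731 + 1/85,549)] = √1.0139 = 1.007, about 0.7% larger.

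Clustering by area is ignored in both.

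**4. Territory of the comparator**

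| Place | Territory |
|---|---|
| Section 1 | UK |
| Section 4, Table 3 note C | England, Wales and Northern Ireland |
| Section 9, Workstream 2 (referring to Table 3) | England |

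Section 9 refers to a table whose stroke control is wider than the territory section 9 states. Neither names the control for the linked mortality data.

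**The case against.** The strongest reply has three parts.

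- **The protocol already asks for unexposed controls.** Section 4 describes trusts where triage is not in use, and section 9 says the same of the comparator. On this view only a dated censoring rule is missing, which a statistical analysis plan commonly supplies, and section 9 also promises early work with data owners and robustness tests. Part of this stands: the intention is clear, and an analysis plan that is not shown may hold such a rule. But the protocol does more than stay silent. It names the rest of London as a control, includes every submitted patient, and removes only the case sites from the national data. Section 9's condition carries no date and does not override those statements.

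- **The roll-outs are only intentions.** This stands. A reader might infer that London and the East of England are already adopting triage and that the estimate is therefore diluted. The protocol does not support that: it reports an aim and a plan, both undated, together with confirmation that nothing of equivalent scale existed elsewhere. A reader might also infer that the East of England contaminates the ambulance outcomes. It is not among the four trusts.

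- **The 85,549 does not decide the primary-outcome comparator.** This also stands. It is an annual stroke-audit count, whereas mortality comes from the linked hospital and death data. Correcting the count alone would leave the mortality control unnamed.

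**Conclusion.** The concern holds as a conditional one. As written, the control rules would keep patients from any London or East of England service that starts before the end of August 2022, contrary to section 9's own requirement of an unexposed control. The bias would be toward no effect, by a factor of about (1 − share of after-period control patients exposed).

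Its size cannot be derived from the documents. Under the assumed ranges the effect retained runs from 50% to 97.5% for ambulance outcomes and from 75% to 98.8% for the national control. It is 100% in both if no roll-out starts in the window. These figures assume that the effect in an adopting area equals that in the case sites. They show what could happen; they do not demonstrate bias in the primary analysis.

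The inconsistency over territory and the missing control for 90-day mortality do not depend on any roll-out. Nothing in the protocol shows which territory is intended.

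**What to change.** 1. **Amend the include-all sentence in section 4, Case sites and controls.** Any control area or hospital that starts prehospital video triage, including a pilot, before the end of August 2022 is excluded from the control for the whole window. If only its months from go-live are dropped, the model must include area fixed effects. Otherwise the area contributes to the before period and not to the after period, and the control's mix changes across the contrast. Matching on patient characteristics such as age and sex would not correct that.
2. **Obtain go-live dates** from the people leading the roll-outs, whom the team already engages. Main analyses run from month 13, that is September 2022, after the window closes, so the dates will be known.
3. **Add a sensitivity analysis** that omits London and the East of England from the controls in which they appear.
4. **State one comparator territory** in section 1, Table 3 note C and section 9, and name the control for the linked HES/ONS mortality data. Restate 85,549 if the chosen territory differs from note C.

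The cost is a short amendment, a list of dates and a modest loss of control data: about a 5% larger standard error for ambulance outcomes if 40% of control calls go, and under 1% for the national control if 25% go.

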2 BACKGROUND AND RATIONALE

Stroke is a major cause of death and disability.^[1] Stroke patients have better care and outcomes if treated in a specialist unit.^[2-5] Not every hospital has a specialist stroke unit: patients are commonly triaged by prehospital clinicians, bypassing the nearest emergency department if a patient is thought to be suffering a stroke. Many patients present with stroke-like symptoms but have another condition which 'mimics' a stroke. This may be difficult to determine in the prehospital setting with the assessment deemed 'false positive',^[6] and the patient making an unnecessary journey to a specialist stroke team when in fact an alternative health care setting may be more appropriate (comprising up to 50% of all presentations to specialist stroke teams). This places avoidable pressure on ambulance and stroke services, with serious implications for quality of care for stroke and non-stroke patients.^[7] Remote prehospital triage may increase appropriate patient transfer, improving effectiveness and efficiency of ambulance, stroke, and other services, and the quality of care and outcomes for stroke and non-stroke patients.

During the first wave of the COVID19 pandemic, ambulance, and stroke teams in North Central (NC) London and East Kent developed and implemented prehospital video triage services, which used digital tools technology to permit remote communication between ambulance clinicians and stroke specialists. Through these services, stroke specialists can assess the patient while the patient is still on scene of the 999 call. The aim was to optimise individual patients' care: to ensure that stroke patients were taken to a stroke unit, and to minimise the number of non-stroke patients making unnecessary journeys to a stroke unit or hospital emergency departments (ED) if they could be managed by their GP or as an outpatient; these issues are important at any time, but became particularly urgent during the pandemic.

Reviewing existing evidence

Through a current service evaluation (discussed below),^[8] the team are conducting a two-phase literature review to assess the existing evidence base. The initial phase was a 'review of reviews' to identify existing systematic, scoping and narrative reviews on prehospital triage for

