Acute stroke system	Centralising	Centralised 2010	Centralising	Centralising
Rurality	Rural	Urban	Rural	Rural

Note. ¹East Kent eligibility was initially for patients where there was diagnostic uncertainty, and changed to all suspected strokes in September 2020.

Workstream 1: implementation and experiences [RQs 1&2; months 1-24]

The study will use a range of qualitative methods to analyse implementation and sustainability of prehospital triage services for stroke, and stakeholder experiences of these services, including patient, carer, and healthcare professional perspectives. The approach will draw on the chosen conceptual framework for implementation and sustainability of digital innovation,^[28] and it will be informed by the developing findings from the team's recent service evaluation of the NC London and East Kent services.

Stakeholder interviews

In each of the four case sites, up to 30 interviews will be conducted with a wide range of stakeholders to ensure suitable coverage of the services studied and the context in which they operate. Interviewees will include stroke and non-stroke (initially suspected to be stroke) patients and their carers, including patients with different decisions resulting from assessment (i.e., transferred to stroke unit, transferred to emergency department, referred to TIA clinic, advised to stay home). The team will work closely with clinical colleagues (including local research nurses) and purposively sample interviewees to ensure that a diverse range of patients and carers is recruited, in order to reflect local socio-demographic factors, including ethnicity, socio-economic status, language capabilities (e.g. non-English speakers) and living situation (e.g. patients who live alone). Interviews will also be conducted with clinical and managerial staff in ambulance services, acute stroke teams, and emergency departments, senior organisational management, and representatives of the wider context (Table 2).

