Note. ^AControl for stroke patients is national, whereas the control for Ambulance data combines four NHS Ambulance trusts –meaning the stroke patient control is proportionally larger than the ambulance data control. ^BStroke case numbers drawn from the Stroke Sentinel National Audit Programme (SSNAP) data for April 2019 to March 2020. ^CNational data cover England, Wales, and Northern Ireland, excluding strokes reported for the case sites. ^DEast Kent data combine strokes reported for two sites: Queen Elizabeth the Queen Mother Hospital and William Harvey Hospital. ^EMaidstone data combine strokes reported for two sites: Maidstone General Hospital and Tunbridge Wells Hospital, the latter of which closed in late 2019, with stroke activity transferred to Maidstone. ^FAmbulance call sample based on estimates of 12 months of calls where ambulance crews have categorised patients as 'suspected stroke/neurological event', as provided by LAS, SECAmb, WMAS, and NEAS.

To study prehospital care, analyses will focus on job cycle time (from 999 call to 'ambulance free' time, where the ambulance is ready for its next dispatch); and initial patient destination. As these patient-level data are not held nationally the team will request these data from local ambulance services identified above. The team have confirmed with these organisations that the data are collected reliably and are available for request; and the costs agreed for these data requests have been included in the budget. Over the course of data requests researchers will work closely with Ambulance service representatives to ensure consistency of definitions and data collection. To study delivery of acute stroke care and stroke patient functional independence, researchers will analyse patient-level stroke national clinical audit data requested from SSNAP, and data collected by stroke teams using prehospital video triage. To study patient outcomes (patient mortality and length of hospital stay), researchers will analyse Hospital Episode Statistics data linked with Office for National Statistics mortality data, requested at patient-level from NHS Digital.

Source	Data	Measures	Time
Local ambulance	Patient-level	Call categorisation, Emergency Operations Centre	Apr 2019-

Table 4.Quantitative data sources

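### Undated centralisation at three of the four case sites, and a stroke-unit closure inside Maidstone's before period, may be read as an effect of triage

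*Protocol*

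**What the plan says.** Table 1 (section 4), with columns in the order East Kent, NC London, Maidstone, Darent Valley, has the row "Acute stroke system Centralising Centralised 2010 Centralising Centralising". Only NC London has a date. The triage start dates in the same column order are "Implemented from Apr-2020 May-2020 Oct-2020 Nov-2020".

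Note E to Table 3 explains that Maidstone's count combines two hospitals, Maidstone General and Tunbridge Wells, "the latter of which closed in late 2019, with stroke activity transferred to Maidstone".

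On the data window, section 4 says "data covering a 40-month period (April 2019 to August 2022 inclusive) will be requested". It sets out no dates for each site but describes the window as a whole as "permitting a minimum of 12 months 'before' data and minimum of 26 months 'after' data".

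Section 9, Workstream 2, compares the four triage areas with the comparator after propensity matching on patient characteristics that triage could not alter, with sex and age as the examples. It then gives the rule for interpretation: "Provided a valid control group has been identified, the difference between the two differences can be said to represent the impact of the intervention". The primary outcome is 90-day mortality. Robustness tests are promised but not described. Workstream 3 takes its effect size from the DiD.

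**The concern.** DiD removes stable differences between sites and trends shared with the comparator. It does not remove a second change that affects the treated sites only. A valid control group, the single condition in the attribution sentence, does not protect against that. Matching on sex and age does not either, because the change belongs to the service and not to the patient.

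The Protocol itself treats service organisation as able to move the outcome. Section 2 states that "Stroke patients have better care and outcomes if treated in a specialist unit", and the reference list includes a DiD study of how centralising acute stroke services affected mortality and length of stay. Here 90-day mortality is primary, and treatment times and patient destination are also analysed. If part of the contrast is reorganisation, a reader deciding whether to adopt triage would be given the wrong cause, and the same error would enter the cost per QALY.

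**Working it through.** **1. Month counts** (Table 1 start dates, window April 2019 to August 2022).

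| Site | Before | After |
|---|---|---|
| East Kent | 12 | 29 |
| NC London | 13 | 28 |
| Maidstone | 18 | 23 |
| Darent Valley | 19 | 22 |

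The stated 12-month minimum before period is reproduced, at East Kent. (The window is 41 months inclusive and the shortest after period is 22 months, so two other stated lengths do not reproduce. Neither affects this point.)

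**2. Where the closure falls.** Maidstone's before period is April 2019 to September 2020. Taking late 2019 to mean that the first month without Tunbridge Wells lies between October 2019 and January 2020 (assumption), 6 to 9 of the 18 before-months precede the closure: 6/18 = 0.33 to 9/18 = 0.50.

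**3. Weight of the sites** (Table 3, annual counts).
- Strokes: 970 + 1,457 + 789 + 515 = 3,731. The three centralising sites: 970 + 789 + 515 = 2,274, or 60.9%. Maidstone alone: 789/3,731 = 21.1%.
- Calls: 1,729 + 2,529 + 2,620 + 984 = 7,862. The three sites: 5,333, or 67.8%. Maidstone alone: 2,620/7,862 = 33.3%.

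**4. How much of a reorganisation effect reaches the estimate.** Let c be the change in an outcome caused by reorganisation, not shared by the comparator. The part that enters a pooled DiD is

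site share × fraction of that site's before period preceding the change × c.

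- Closure only, Maidstone's own DiD: 0.33c to 0.50c.
- Closure only, pooled stroke DiD: 0.211 × 0.33 = 0.07c to 0.211 × 0.50 = 0.11c.
- Closure only, pooled ambulance outcomes: 0.333 × 0.33 = 0.11c to 0.333 × 0.50 = 0.17c.
- Upper bound, all three sites changing fully at triage start: 0.61c for strokes.

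Placing the closure a month earlier, at the start of September 2019, leaves 5 pre-closure months and lowers the stroke figure to 5/18 × 0.211 = 0.06c.

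**5. Illustration.** The Protocol gives no value for c. If c were 1 to 2 percentage points of 90-day mortality (assumption), the closure alone would contribute 0.07 to 0.21 points to the pooled estimate, and the upper bound would be 0.6 to 1.2 points.

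**6. Comparison with sampling error.** SE = √[p(1−p)(1/n₁ + 1/n₂ + 1/n₃ + 1/n₄)], with annual counts scaled by months/12, the national control (85,549 a year) split 14/27 months, p assumed at 10% to 25%, and patients treated as independent.
- Pooled: 4,547 before and 8,200 after; SE 0.57 to 0.82 points.
- Three Kent sites: 2,969 and 4,801; SE 0.71 to 1.03 points.
- NC London: 1,578 and 3,400; SE 0.92 to 1.33 points.

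In this illustration the closure alone is well below one pooled SE. The upper bound with c = 2 exceeds one.

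**The case against.** Several points on the other side are sound.

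- **Timing.** A reader might infer that all three Kent sites demonstrably reorganised while triage was running, so that their contrast simply is triage plus reorganisation. The Protocol does not show this. Centralising is undated; that it overlaps the window is inferred from its use as current status in a document that reports a review completed in September 2021. The one dated change is Tunbridge Wells, some 9 to 12 months before Maidstone's triage start, so it contaminates part of a baseline and does not coincide with triage.
- **Size.** A reader might take 0.6 to 1.2 mortality points as the expected bias. It is a ceiling under an assumed c and a full switch at triage start in all three sites.
- **Destination.** It is tempting to say that the closure shifts the destination outcome mechanically. Suspected strokes redirected to Maidstone still reach a hospital with a stroke unit. Only patients still taken to Tunbridge Wells would change category, and their number is not given.
- **Control.** Destination and job-cycle outcomes use a control from four ambulance trusts, including the rest of the Kent sites' own ambulance service; the national control applies to in-hospital stroke care. Whether control areas were also reorganising is not stated.
- **Room left in the plan.** Pooling is implied by the wording of the comparison and not stated. Attribution is conditional, robustness tests are promised, section 4 discloses that the sites differ in stroke system, and Workstream 1 builds site timelines. Detailed modelling may sit in a SAP.

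These limit the size and certainty of the problem but do not remove it. The Protocol itself fixes the kind of matching variable and the attribution rule, while recording a site-level change that neither can handle. Unspecified robustness tests do not fill that gap.

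**Conclusion.** The concern holds in a limited form. As written, the attribution rule would let a service-level change in the treated sites be reported as an effect of triage. The exposure is wide, at 61% of case-site strokes and 68% of calls. The one dated event passes only about 7% to 11% of its effect into a pooled stroke estimate (11% to 17% for ambulance outcomes). The larger but undated risk is centralisation at all three sites, bounded at about 0.6c for strokes.

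This rests on four assumptions: late 2019 as defined above, annual counts as weights, a pooled contrast, and a reorganisation effect not shared by the comparator. The Protocol supports no statement about the sign or size of c, so it cannot be said that triage will look better or worse than it is.

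**What to change.** In section 9, Workstream 2:

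1. Report the DiD separately for NC London and for the three Kent sites, beside any pooled figure. This is for transparency and should not become a rule that agreement proves the effect. NC London is imprecise and also differs in ambulance service and rurality and, from Maidstone and Darent Valley, in assessor and hours.
2. Establish the dates of stroke-unit closures and moves in the case-site catchments. The Workstream 1 timelines cover triage implementation, so these dates would have to be added. Include a dated term for the Tunbridge Wells closure and for any other change that does not coincide with triage start. One that does coincide cannot be separated from triage.
3. As a sensitivity analysis only, start Maidstone's before period after the closure. This leaves about 9 to 13 months (18 less 9, to 18 less 5), possibly below the stated 12-month minimum. Six of them, April to September 2020, fall in the pandemic period in which the first services were launched.
4. Qualify the attribution sentence: where reorganisation and triage cannot be separated, describe the Kent and pooled estimates as triage plus concurrent reorganisation, and carry that wording into the cost-effectiveness results.

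The cost is some added wording, a little more analysis of data already requested, the work of dating the service changes, and wider intervals: SE about 0.9 to 1.3 points for NC London against 0.6 to 0.8 pooled, on the assumptions in the working.
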